3.2 RISK MANAGEMENT

All efforts will be made to minimize the identified risks by selecting Investigators, team members and study sites who meet the following criteria:

- Interventional Cardiologist - must be board certified (or equivalent), experienced with performing transcatheter heart valve repair and replacement, and skilled in percutaneous coronary interventions and structural heart interventions.
- Access Management Physician - must be board certified (or equivalent), experienced with access management (subclavian/axillary vein access) and right heart interventions.

There will be strong interdepartmental collaboration between interventional cardiology and cardiovascular surgery operators and a designated team of nurses, technicians and colleagues from supporting medical disciplines (e.g., anesthesiologist, heart failure specialist, echo-cardiographer, radiologist).

The procedural location is to be an operating room, catheterization lab or hybrid operating room with fluoroscopic and echocardiographic imaging capabilities.

Adverse events will be reviewed by the Study Sponsor, Data Safety Monitoring Board and Clinical Events Committee as defined in the respective charters.

3.3 BENEFITS

The clinical benefits of using the FORMA System for the treatment of tricuspid regurgitation are not known at the present time. There are no guaranteed benefits from participation in this clinical study and being treated with the investigational FORMA System.

Tricuspid valve repair with the FORMA System may result in one or more of the following benefits for patients typically considered high risk for tricuspid repair or replacement: decrease in tricuspid regurgitation, acute alleviation of symptoms related to tricuspid insufficiency, and/or improved morbidity and mortality.

Information gained from the conduct of this study may be of benefit to other people with the same medical condition in the future as the indication for the system is expanded.

3.4 JUSTIFICATION

This study, the first with the FORMA System, is designed as a multi-site, prospective, early feasibility study. This study is designed to confirm that the safety and function observed in non-clinical testing is also observed in a limited human population.

The treatments currently available for this patient population include palliative medical therapy and high-risk surgical replacement or repair of the tricuspid valve. Treatment with the FORMA System may enable patients with tricuspid regurgitation to undergo tricuspid valve repair via a minimally invasive approach.

4 STUDY OBJECTIVES

The objectives of this early feasibility study are to:

- Evaluate the safety and function of the FORMA System
- Provide guidance for future clinical study designs utilizing the FORMA System
- Provide guidance for future FORMA System development efforts

5 STUDY ENDPOINTS

5.1 FEASIBILITY ENDPOINTS

5.1.1 SAFETY ENDPOINT

Composite of major adverse events (MAE) defined as cardiovascular mortality, myocardial infarction, new need for renal replacement therapy, severe bleeding, re-intervention and major access site and vascular complications at 30 days.

5.1.2 PERFORMANCE ENDPOINT

5.1.2.1 Device Success

Device is deployed as intended and the delivery system is successfully retrieved as intended at the time of the patient's exit from the cardiac catheterization laboratory.

5.1.2.2 Procedural Success

Device success with evidence of TR reduction as evidenced by a relative reduction in EROA of $\geq 30\%$ from baseline to discharge and without the need for a surgical or percutaneous intervention prior to hospital discharge.

5.1.2.3 Clinical Success

Procedural success without MAEs at 30 days. (MAEs: cardiovascular mortality, myocardial infarction, new need for renal replacement therapy, severe bleeding, re-intervention and major access site and vascular complications)

5.1.3 OTHER ENDPOINTS

5.1.3.1 Echocardiographic parameters

- A. Reduction in TR severity (assessed by TR grade and quantitative measures) as assessed by TEE pre- and post-implant in the procedure room.

Additional echocardiographic parameters will be compared to baseline:

- B. TTE parameters assessed at baseline, discharge, 30 days, 6 months, 1 year and annually until 3 years post procedure.
1. TR grade- qualitative assessment
 2. Vena Contracta (2D)
 3. EROA (PISA/2D or 3D/3D color doppler)
 4. Regurgitant volume
 5. Tricuspid annular diameter (end-diastolic – S-L)
 6. Tricuspid annular area (2D/3D mid-diastolic)
 7. Tenting area and distance
 8. Forward stroke volume
 9. RV dimensions
 10. Right atria volume
 11. Left ventricular Ejection Fraction
 12. Inferior Vena Cava dimensions/respiratory variations
 13. Hepatic vein flow reversal
 14. Pulmonary artery pressure (peak)
 15. Right ventricular function

6 STUDY DESIGN

This is a multi-site, prospective, early feasibility study designed to evaluate the safety and function of the FORMA System.

A total of sixty patients will be enrolled in the study. All enrolled study patients will be assessed for clinical follow-up at the following intervals: 1 month, 6 months, 1 year and annually for 3 years post implant procedure.

A description of each study visit and required study procedures is included in Section 8.0, Procedures and Methods. In addition, a summary of required procedures is listed in Table 13.

7 PATIENT POPULATION

7.1 DEMOGRAPHIC AND CLINICAL CHARACTERISTICS

This clinical study is for adult patients with clinically significant, symptomatic, functional, tricuspid regurgitation who are deemed to be candidates for transcatheter tricuspid valve repair by the local Heart Team.

All patients who meet the initial study eligibility requirements will be evaluated for study participation.

Candidates for this study must meet all of the following inclusion criteria and none of the exclusion criteria:

7.2 INCLUSION CRITERIA

The Investigator has the responsibility of screening potential patients to determine if the patients meet all the inclusion criteria. The following are requirements for entry into the study:

1. Age \geq 18 years old
2. Symptomatic severe (Stage D) functional, tricuspid regurgitation (per applicable guidelines)
3. Symptomatic despite medical therapy; patient must be on diuretic therapy.
4. The local site Heart Team determines that the patient is appropriate for transcatheter tricuspid repair
5. Patient is willing and able to comply with all specified study evaluations and provides written informed consent.

7.3 EXCLUSION CRITERIA

The Investigator at the study site must exclude patients if any of the exclusion criteria are present. The following are the criteria for exclusion from participating in the clinical study:

1. Echocardiographic/CT parameters (any of the following):
 - a. Vessel access or right heart anatomy precluding proper device introduction, deployment and function
 - b. LVEF $<$ 30%
 - c. Severe right ventricular dysfunction as assessed by the core lab
 - d. Patients with systolic pulmonary artery pressure $>$ 60 mmHg
2. Primary tricuspid disease (e.g. rheumatic, myxomatous degeneration, tricuspid valve prolapse, tricuspid stenosis)
3. Previous tricuspid leaflet repair or tricuspid valve replacement
4. Presence of two or more trans-tricuspid leads or any single trans-tricuspid lead:

- a. Precluding proper placement of or interferes with device
 - b. Implanted within the last 180 days
 - c. With pacemaker dependency
5. Severe aortic, mitral and/or pulmonic valve stenosis and/or regurgitation
 6. Active endocarditis within 90 days of the scheduled implant
 7. Significant pericardial effusion
 8. Intra-cardiac mass, thrombus, or vegetation
 9. Untreated clinically significant coronary artery disease requiring revascularization
 10. Recurrent (>2 per 12 months) hospitalizations or ER visit for COPD exacerbation
 11. MI or known unstable angina within 30 days prior to the index procedure
 12. Any therapeutic invasive cardiac procedure within 30 days prior to the index procedure, or any dual anti-platelet therapy (DAPT) requirement which cannot be interrupted for 7 days
 13. Any cardiac surgery, within 3 months prior to procedure
 14. Hemodynamic instability or on IV inotropes within 30 days of the scheduled implant
 15. Severe uncontrolled hypertension (SBP \geq 180 mmHg and/or DBP \geq 110 mm Hg)
 16. Cerebrovascular Accident (CVA) or TIA within the past 30 days
 17. Kidney dysfunction with estimated Glomerular Filtration Rate (eGFR) < 30 ml/min/1.73 m² or patient is on chronic dialysis
 18. Any physical impairment which limits the patient's capacity to complete functional testing due to other medical conditions independent of their TR (e.g. orthopedic condition)
 19. Significant frailty (i.e. Katz Index of Independence in Activities of Daily Living (ADL) \leq 2) within 90 days of scheduled implant procedure
 20. Continuous home oxygen for primary severe COPD
 21. Chronic anemia (Hgb < 9 g/dL) not corrected by transfusion
 22. Thrombocytopenia (Platelet count < 100,000/mm³) or thrombocytosis (Platelet count > 750,000/mm³)
 23. Bleeding disorders or hypercoagulable state
 24. Active peptic ulcer or active gastrointestinal (GI) bleeding within 90 days of the scheduled implant
 25. Cardiac cachexia
 26. Contraindication to anticoagulants or antiplatelet agents
 27. Currently or history of IV drug use
 28. Pregnant or lactating; or female of childbearing potential with a positive pregnancy test 24 hours before any study-related radiation exposure

29. Patients in whom transesophageal echocardiography is contraindicated
30. Known allergy to cobalt chromium, nitinol, titanium or contrast agents that cannot be adequately pre-medicated.
31. Known hypersensitivity or contraindication to procedural medications which cannot be adequately managed medically
32. Impaired judgment and/or is undergoing emergent or urgent treatment for tricuspid insufficiency
33. Currently participating in another investigational drug or device study that has not completed the primary endpoint or that clinically interferes with the endpoints of this study
34. Co-morbid condition(s) that, in the opinion of the Investigator, limit life expectancy to < 12 months
35. Co-morbid condition(s) that, in the opinion of the investigator, could limit the patient's ability to participate in the study, including compliance with follow-up requirements, or that could impact the scientific integrity of the study
36. Patient is under guardianship

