8.3 BASELINE EVALUATION

1. Informed consent will be obtained from all patients who have been determined to be eligible study candidates and agreed to participate in the study.
2. Patient demographics and medical history (includes 12 months prior hospitalizations including emergency department (ED) visits, paracentesis)
3. Clinical Evaluation (includes vital signs, concomitant medical treatments, edema grading, ankle circumference measurements, weight and height) and NYHA classification
4. Administration of Health Status Questionnaires (e.g., SF-12, KCCQ)
5. Administration of Six Minute Walk Test (6MWT)
6. Administration of Katz Index of Independence in Activities of Daily Living (ADL)
7. Administration of Canadian Study of Health and Aging (CSHA) Clinical Frailty Scale[®]

8. Administration of Patient Edema Questionnaire
9. Administration of Patient Preference Survey
10. Modified Rankin score (mRS) *
11. Clinical Laboratory Tests
 - a. The following lab tests shall be done within 30 days of the scheduled implant procedure:
 - i. Troponins and cardiac enzymes (CK-MB) - *MI within 30 days of the scheduled implant procedure is an exclusion from study participation*
 - b. The following lab tests shall be done \leq 2 weeks before implant procedure:
 - i. CBC and platelet count
 - ii. Complete metabolic panel
 - iii. Liver panel including gamma-glutamyl transferase (GGT)
 - iv. Serum Creatinine and eGFR
 - c. The following lab tests shall be done \leq 48 hours before the implant procedure:
 - i. β HCG for women who are not sterile or post-menopausal- *positive result is an exclusion from study participation.*
 - ii. INR and PTT/aPTT
12. Standard 12-lead Electrocardiogram (ECG)
13. Comprehensive Transthoracic Echocardiogram (TTE must be collected per Echocardiography Acquisition Protocol) ⁶.
14. Transesophageal Echocardiogram (TEE), including but not limited to transgastric views.
15. All candidates must have pre-implant procedure imaging (e. g., Computed Tomography (CT) Angiogram), that captures the anatomy of the subclavian and axillary veins, superior vena cava, tricuspid valve and sub-valvular structures/anatomy, right atrium and right ventricle.
16. Invasive Hemodynamic Monitoring/Right Heart Catheterization that should include, but is not limited to, right atrial pressure (RAP), PAP, right ventricle pressure (RVP), cardiac output (CO), and PVR measurements.⁷

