| 
 • Inclusion/exclusion evaluation • Informed consent • Age • Gender • Height • Weight | 
 • Local Heart Team determination • Patient demographics • Medical history (e.g., EuroSCORE, STS Score) /prior cardiovascular interventions / surgeries / 12-month prior hospitalizations and paracentesis • Vital signs (Blood pressure, heart rate) • Edema grading & ankle circumference measurements • Concomitant Medications and doses • NYHA classification • Echocardiographic measurements (TTE & TEE), tricuspid regurgitation & heart function • CT • Coronary angiogram • Venogram (in patients with cardiac leads) if required | 
Within 30 days of procedure:
 
 • Date of blood draw • Troponin¹ and CK-MB¹ 
Within ≤ 2 weeks of procedure:
 
 • Date of blood draw • Serum Creatinine & eGFR • WBC • RBC • Hematocrit • Hemoglobin • Platelets • ALT/SGPT • AST/SGOT • Bilirubin • LDH • GGT • ALP • Albumin • Sodium & potassium • Urea 
Within ≤ 48 hours of procedure:
 
 • INR & PTT/aPTT • βHCG, if applicable² |

| General Information | Clinical Information | Laboratory Measurements |
|---------------------|---|-------------------------|
| | 
 • Interrogation of pacemaker leads • Invasive Hemodynamic Monitoring/Right Heart Catheterization including pressure measurements • ECG results • Six minute walk test • Katz Index (ADL) test • CSHA Frailty scale • KCCQ & SF-12 questionnaires • Edema Questionnaire • Preference Survey • mRS (if applicable) | |

1. MI within 30 days of the scheduled implant procedure is an exclusion from study participation
2. A positive result is an exclusion from study participation

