8.7.1 VISIT & ASSESSMENT WINDOWS

Post-procedure follow up visits will be performed on all implanted study patients at 1 month, 6 months, and annually for 3 years post implant procedure intervals as illustrated in Table 11 below:

Table 11 – Follow-up Visit Windows

| Scheduled Follow-up Interval | Follow-up Window |
|-----------------------------------|------------------|
| 1 month (30 days) | ± 7 days |
| 6 months (180 days) | ± 30 days |
| Annually (365 days) up to 3 years | ± 45 days |

Table 12: Screening/Baseline Assessment Windows

| Assessment | Window |
|------------------------------------|--|
| TTE* | Within 60 days of submission to Sponsor |
| TEE** | Within 90 days of submission to Sponsor |
| Hemodynamic Monitoring | Within 90 days of scheduled implant procedure ⁷ |
| Venogram (pacemaker lead patients) | Within 90 days of scheduled implant procedure if venous patency cannot be determined by CT |
| CT Angiogram** | Within 180 days of submission to Sponsor |
| Coronary Angiogram | Within 180 days of scheduled implant procedure |
| Pacemaker interrogation | Within 180 days of scheduled implant procedure |

* TTE must be conducted after informed consent and must be collected according to echo core lab acquisition protocol.

**pre-existing TEE/CT image of adequate quality capturing required anatomy for assessment can be used.

Note: For all imaging (TTE, TEE, CT angiogram, coronary angiogram), if imaging is deemed incomplete or inadequate for assessment, repeat imaging may be required.

Note: Procedure should be scheduled within 90 days of consent.

During the follow up visits, medical information, findings and results will be entered in the appropriate electronic case report forms.

Study patients who have signed the Informed Consent, have met all eligibility criteria, and have the study procedure attempted (at least skin incision to introduce the FORMA system) are considered enrolled in the study.

Patients who enter the procedure room but who do not have the study procedure attempted (at least skin incision to introduce the FORMA system) will be classified as

⁷ If the screening echo confirms the PAP meets the study criteria, the right heart catheterization/hemodynamic assessment at the baseline evaluation may be waived.

“non-implanted” and will be followed 30 days for safety. These patients will be exempt from all other study follow up visit procedures.

Final

Table 13 – Summary of Required Study Procedures

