| STUDY PROCEDURES | BASELINE | IMPLANT PROCEDURE ¹ (Day 0) | DAY 1 (24-48 hrs) | DISCHARGE ² | 1 MONTH (30 ± 7 days) | 6 MONTHS (180 ± 30 days) | ANNUAL (for 3 yrs) (365 ± 45 days) |
|---|----------------|---|----------------------|------------------------|---------------------------|-----------------------------|--|
| Informed Consent | X | | | | | | |
| Patient Demographics & Medical History | X | | | | | | |
| Clinical Evaluation/Concomitant Medications ³ | X | | X | X | X | X | X |
| Edema grading, ankle circumference measurements & Patient Edema Questionnaire | X | | | X | X | X | X |
| Hospitalizations &/or clinic visits & paracentesis | X | | | | X | X | X |
| NYHA Class Assessment | X | | | | X | X | X |
| Health Status Questionnaires KCCQ, SF-12 | X | | | | X | X | X |
| Six Minute Walk Test | X | | | | X | X | X |
| Katz Index (ADL), Clinical Frailty Score© | X | | | | | | |
| Patient Preference Survey | X | | | | | | |
| Safety Evaluation | | X | X | X | X | X | X |
| Pacemaker interrogation (pacemaker patients) | X | | | | | | |
| Coronary angiogram (within 1 year of procedure) | X | | | | | | |
| Complete Metabolic Panel and Liver Panel | X | | X | X | X | X | X |
| CBC and Platelet Count | X | | X | X | X | X | X |
| INR & PTT/aPTT | X | | X | X | X | X | X |
| βHCG | X ⁴ | | | | | | |
| Serum creatinine and eGFR | X | | X | X | X | X | X |
| Troponins and CK-MB | X | | X | X ⁵ | | | |
| ECG | X | | X | X | X | X | X |
| Transesophageal Echocardiogram | X | X | | | | | |

¹ Implant procedure should be scheduled within 90 days of consent. Patients who enter the procedure room but who do not have the study procedure attempted (at least skin incision to introduce the FORMA System) will be classified as “non-implanted” and will be followed 30 days for safety. These patients will be exempt from all other study follow up visit procedures.

² Discharge from hospital/unit post implant procedure.

³ No changes in diuretics are allowed for at least 3 months post procedure unless patient presents with severe hypotension.

⁴ βHCG for women who are not sterile or post-menopausal.

⁵ Only required if an elevation was noted post implant (within 48 hours).

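### The pregnancy exclusion is tied to any study radiation, but the only scheduled βHCG test is tied to the implant, so baseline imaging done for the study after consent has no test scheduled before it.

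*Protocol*

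**What the plan says.** Four places in the protocol bear on this point, and the SAP does not address it.

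- **Eligibility.** Exclusion 28, worded alike in the synopsis and Section 7.3, covers pregnant or lactating patients and also a woman of childbearing potential with a "positive pregnancy test 24 hours before any study-related radiation exposure".
- **Schedule of tests.** Section 8.3, item 11c, places βHCG among the laboratory tests done at most "48 hours before the implant procedure". Table 6 lists it under the heading "Within ≤ 48 hours of procedure".
- **Summary table.** Table 13 has one mark for βHCG, in the Baseline column. Its footnote, "βHCG for women who are not sterile or post-menopausal", says who is tested but gives no hours and no link to imaging.
- **Baseline imaging.** Section 8.3, item 15, states that "All candidates must have pre-implant procedure imaging" and gives CT angiography as the example. Item 17 allows a venogram in some patients with cardiac leads, and item 19 lists a coronary angiogram. Section 8.7.1 adds "Procedure should be scheduled within 90 days of consent".

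**The concern.** The exclusion protects against exposing an unrecognised pregnancy to radiation given for the study. To apply it, a site needs a test result before the exposure. The schedule supplies one result, and only in the last two days before the implant. CT findings feed the eligibility decision (exclusion 1), and Table 12 times the CT against submission of the case to the sponsor, so a CT done for the study would ordinarily come well before those two days.

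A coordinator who works from Section 8.3, Table 6 and Table 13 could therefore send a woman of childbearing potential for study imaging with no pregnancy test on file, and would have departed from nothing in the schedule. Such cases may be rare, but the possible harm in one of them is serious. The two intervals also leave a monitor unsure how to judge a test done on the second day before the implant.

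**Working it through.** The plan gives no figure to reproduce. The check sets the windows side by side, counting back from the implant as Day 0.

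**Inputs**

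| Item | Timing | Source |
|---|---|---|
| Pregnancy exclusion | 24 hours, before any study radiation | Synopsis; Section 7.3, item 28 |
| Only scheduled βHCG | at most 48 hours before implant: Day −2 to Day 0 | Section 8.3, item 11c; Table 6 |
| βHCG in the summary table | Baseline, no hours | Table 13 |
| Consent to implant | up to 90 days | Section 8.7.1 |
| CT angiogram | within 180 days of submission to the sponsor; an existing scan may be used | Table 12 |
| Coronary angiogram | within 180 days of implant (Table 12) or 1 year (Table 13) | Section 8.7.1 |
| Venogram | within 90 days of implant, only if CT cannot settle venous patency in a lead patient | Table 12 |
| Baseline right heart catheterization | may be waived if the screening echo settles the pulmonary pressure criterion | Footnote 7 |

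**Step 1: which imaging counts.** Section 8.1 requires consent before any study procedure. Study-related radiation is therefore taken here as imaging newly done after consent. Scans and angiograms from before consent fall outside the exclusion's trigger.

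**Step 2: longest gap for that imaging.** If consent and imaging fall on the same day and the implant is 90 days later, the imaging is at Day −90.

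- To the opening of the test window: 90 − 2 = 88 days.
- To a test on the day of implant: 90 − 0 = 90 days.

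Imaging can thus precede the test by up to about 88 to 90 days. A venogram at the edge of its own 90-day window gives the same result. Shorter consent-to-implant intervals, or later imaging, shrink the gap in step. It closes only if the imaging falls after the test, inside the last 48 hours.

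**Step 3: the implant itself.** Section 8.6 calls for fluoroscopic imaging, so the implant is also a radiation exposure. Reading exclusion 28 as within 24 hours:

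- a test 25 to 48 hours before implant meets Section 8.3 and Table 6 but not exclusion 28;
- a test within 24 hours meets both.

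**The case against.** The strongest reply is that exclusion 28 is binding in its own right. Section 7.3 obliges the investigator to exclude anyone who meets a criterion, item 28 names its own trigger, and nothing in Section 8.3 forbids an earlier or additional test. Table 13 even lists βHCG at Baseline beside the imaging, without an hour limit. A careful site would test before study imaging and again before the implant. This stands: a reader might infer that the exclusion cannot be applied to baseline imaging at all, and the documents do not support that. What remains is that the schedule omits a test which the criterion presupposes. The separate exclusion of known pregnancy does not fill that gap, because the test exists to find pregnancies not yet recognised.

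A second reply is that much baseline imaging may not be study radiation. The CT may already exist, the coronary angiogram may predate consent, the venogram is conditional, and baseline right heart catheterization may be waived and is nowhere said to involve radiation. This also stands, and it limits the point to imaging newly done after consent. For the same reason the angiogram windows should not be turned into gaps of 178 days (180 − 2) or 363 days (365 − 2). With implant within 90 days of consent, angiograms that old would predate consent.

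A third reply is that 24 and 48 hours are compatible for the implant, since one test can satisfy both. That is right. For the implant, one passage is looser than the other, and the two do not exclude each other.

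**Conclusion.** The point holds as an internal inconsistency with a safety implication. The exclusion and the schedule of tests name different anchors and different intervals. As a result, CT, coronary angiography or venography newly done for the study after consent has no scheduled pregnancy test before it. The gap can reach about 88 to 90 days. That maximum assumes imaging on the day of consent and the full 90-day interval, which the protocol words as a recommendation.

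The conclusion also assumes that imaging from before consent is not study-related, and that the schedule as printed is complete. The sample consent form was not available for checking. The documents do not say how many enrolled women would be of childbearing potential. The number is probably small, but no figure can be put on it.

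Nothing here touches the sample size of 60 or any endpoint analysis.

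**What to change.** Reconcile exclusion 28 (synopsis and Section 7.3) with Section 8.3 item 11c, Table 6 and the βHCG row and footnote of Table 13. All of them should state the same anchor, either any study-related radiation or the implant, and the same window. The sponsor must decide which timing applies; this review does not choose between them. Whatever is decided, the schedule should show each test that the criterion relies on, so that a site working from the tables alone reaches the same result as one working from the eligibility list.

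The cost is a wording change in the protocol. Depending on the sponsor's decision, it may add a test for the women concerned. The SAP needs no change.
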